	Dose/dosage:	Single-dose of 100 mg Multi-dose: 100mg OD (one group) vs 100mg BID (second group)
	Administration:	Single-dose of 100 mg Multi-dose: 100mg OD (one group) vs 100mg BID (second group)
Criteria for evaluation:	Dose/dosage:	Coenzyme Q10 Miniactive Retard 100mg capsules, in a vegetable case containing 30 capsules
	Administration:	po (oral formulation)
COQUN ORAL FORMULATION level of plasma concentration:	
- single-dose phase; 24 adult healthy subjects will be given a dose of 100 mg of COQUN ORAL FORMULATION and plasma coenzyme Q10 will be measured over the next 12 hours: at 1, 2, 4, 8 and 12 hours after intake. Pharmacokinetic properties including area under the curve (AUC), maximum plasma concentration (Cmax), time to maximum plasma concentration (Tmax) and elimination half-life (t 1/2) will be measured
 
- multidose-dose phase; 12 adult healthy subjects will be given OD 100mg of COQUN ORAL FORMULATION, after dinner (group A), while the other group of 12 adult healthy subjects will be given BID a dose of 100 mg of COQUN ORAL FORMULATION, after lunch and after dinner (group B); plasma coenzyme Q10 will be measured over the next 4 weeks. Pharmacokinetic properties including area under the curve (AUC), maximum plasma concentration (Cmax), time to maximum plasma concentration (Tmax) and elimination half-life (t 1/2) will be measured.
	
Safety:	Safety will be monitored through vital signs, physical exams, clinical laboratory tests (hematology, serum chemistry), and adverse events including assessment of relationship to the IP.	

	Study Title	Bioavailability Study of COQUN ORAL FORMULATION (CoQ10) administered in Healthy Adults (CoQ10-01)			
	Study ID	VF-BAQ10/2018		Sponsor:	VISUFARMA SpA
	Date	March 03, 2018		Vers.	Final

Statistical methods:	Due to the explorative aim of the study, descriptive statistics and confidence intervals at 90% level will be provided. In particular, continuous variables will be presented as arithmetic mean values \pm standard deviation (SD) and median values with interquartile range; geometric means will be provided as well; for categorical variables absolute and percentage frequencies will be provided.			
-----------------------------	---	--	--	--

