6.3 Risk/Benefit Consideration

Taking 100 mg a day or more of CoQ10 has caused mild insomnia in some people and research has detected elevated levels of liver enzymes in people taking doses of 300 mg per day for long periods of time. Liver toxicity has not been reported.

Other reported side effects include rashes, nausea, upper abdominal pain, dizziness, sensitivity to light, irritability, headache, heartburn, and fatigue.

Medicines for high cholesterol (statins) and medicines that lower blood sugar cause a decrease of CoQ10 levels and reduce the effects of CoQ10 supplements. CoQ10 can reduce the body's response to the blood thinner (anticoagulant) medicine warfarin (Coumadin) and can decrease insulin requirements in people with diabetes.

Many factors can affect the Q10 blood level of people who are not taking a Q10 supplement: age, diet, disease, medications (for example, statin medications).

	Study Title	Bioavailability Study of COQUN ORAL FORMULATION (CoQ10) administered in Healthy Adults (CoQ10-01)		
	Study ID	VF-BAQ10/2018	Sponsor:	VISUFARMA SpA
	Date	March 03, 2018	Vers.	Final

For this study, the subjects will be screened in order to be healthy, with no concomitant diseases, who will receive 100mg or 200mg of COQUN ORAL FORMULATION for 1 month and will be treated appropriately and constantly monitored so that benefits outweigh potential risks for the subjects.

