7.2 VARIABLES

Primary Variable

Pharmacokinetic properties:

- Area under the curve (microg/ml x h): ≥ 5
- Cmax: $\geq 0,8$
- Tmax: ≥ 3
- elimination half-life (t 1/2)

Secondary Variable(s)

The secondary variables are the ones regarding safety which will be monitored through vital signs, physical exams, ECGs, clinical laboratory tests and adverse events, as follows:

- following a single oral dose of 100mg COQUN ORAL FORMULATION
- in 1 month period of daily oral intake of 100mg OD or BID COQUN ORAL FORMULATION

Symptoms and signs like mild insomnia, elevated levels of liver enzymes, rash, nausea, upper abdominal pain, dizziness, sensitivity to light, irritability, headache, heartburn, and fatigue will be closely monitored.

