10.6.9 Laboratory assessments

Screening and early morning assessments will be performed at V1 (screening) and each of the ambulatory visits on Day 0, 7, 14 and Day 28 (EOS).

Subjects will be required to be fasted for at least 8 hours before blood sampling.

Hematology

RBC count, WBC count (total, i.e, leucocyte count and differential, i.e., neutrophils, eosinophils, basophils, lymphocytes, monocytes), platelet count, hemoglobin, hematocrit.

Blood sample handling

All blood samples will be taken by either direct venipuncture or an indwelling cannula inserted in a forearm vein. When not using a cannula, the location of venipuncture will be varied from one draw to the next to minimize subject discomfort. Blood samples will be taken in 3.5 ml Vacutainers® (serum chemistry), 3 ml EDTA Vacutainers (hematology) and 3 ml Vacutainers (glucose).

A copy of laboratory parameters normal ranges will be filed in the TMF and in the ISF.

The investigator will evaluate the clinical significance of each laboratory value outside of the reference range. Values which are considered clinically significant and/or IP-related will be noted in the CRF. The investigator may choose to repeat any abnormal result ONCE in order to rule out laboratory error. "NCS" will be entered on the patient chart and on the laboratory CRF page for all laboratory values which are outside the reference range but are judged "not clinically significant" The physician making the assessments shall be specified on the patient chart.

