10.7 Premature Termination of the Study

The subject may withdraw from the study any time without giving reasons and without any disadvantageous consequences for his subsequent medical care. Furthermore, the subject should be withdrawn from the study if the investigator has the impression that it would be to the subject's detriment to continue the study.

In case of premature termination from the study the investigator should perform the following:

- physical examination
- vital signs (blood pressure, heart rate temperature and respiratory rate)
- body measurements (weight)

	Study Title	Bioavailability Study of COQUN ORAL FORMULATION (CoQ10) administered in Healthy Adults (CoQ10-01)		
	Study ID	VF-BAQ10/2018	Sponsor:	VISUFARMA SpA
	Date	March 03, 2018	Vers.	Final

- 12 lead ECG
- blood laboratory analysis (Hematology,) to be performed at investigator discretion whenever indicated by the subject health status
- record of concomitant medication
- adverse events

Note: If the subject did not receive any IP (i.e., premature termination between the ICF signature and the single dose phase) no further examination are necessary to be performed and subject will be declared screening failure.

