12.9 Analysis of Safety Variables

12.9.1 Adverse Events

	Study Title	Bioavailability Study of COQUN ORAL FORMULATION (CoQ10) administered in Healthy Adults (CoQ10-01)		
	Study ID	VF-BAQ10/2018	Sponsor:	VISUFARMA SpA
	Date	March 03, 2018	Vers.	Final

Safety will be monitored through vital signs, physical exams, clinical laboratory tests (hematology) and adverse events including assessment of relationship to the IP.

Analysis of safety will be performed on the safety set.

The recorded adverse events will be coded according to MedDRA. The adverse events will be summarized by treatment, System Organ Class, preferred-term and intensity.

Nature, incidence and intensity, as well as the investigator's and the sponsor's causality assessment will be reported for each treatment-emergent adverse event. Descriptive summary statistics, e.g., with regard to the incidence of symptoms and the causality assessment, will be presented for the period between V1-V5. Furthermore, all non treatment-emergent adverse events during pre-treatment will be reported between the ICF signature and the first IP intake at V1.

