Number of deaths	n (%)	XXX (X.X%)	XXX (X.X%)	XXX (X.X%)

N: Number of subjects in specified treatment group

n: Number of subjects with data available

%: Percentage based on N

Notes: a) serious AE are AE with seriousness recorded as "yes";
b) related AE are AE with relationship with study device recorded as "definitive", "probable", "possible";
c) severe AE are AE with severity recorded as "severe", "life threatening or disabling";
d) Subjects who prematurely terminated the Study Due to AE are defined as those subjects with an adverse event for which the reason for early termination in the CRF end of study has been recorded as "adverse event".

RUN: DDMMYYYY HH:MM <1MED > Page X of Y

Table 20. AEs of Special Interest in the Single Dose Phase (Safety set)

	Statistic	Treatment A (N=XXX)	Treatment B (N=XXX)	Total (N=XXX)
Total	n (%)	XXX (XXX.X%)	XX (XXX.X%)	XXX (XXX.X%)
Insomnia	n (%)	XX (XX.X%)	XX (XX.X%)	XX (XX.X%)
Elevated levels of liver enzymes	n (%)	XX (XX.X%)	XX (XX.X%)	XX (XX.X%)
Rash	n (%)	XX (XX.X%)	XX (XX.X%)	XX (XX.X%)
Nausea	n (%)	XX (XX.X%)	XX (XX.X%)	XX (XX.X%)
Upper abdominal pain	n (%)	XX (XX.X%)	XX (XX.X%)	XX (XX.X%)
Dizziness	n (%)	XX (XX.X%)	XX (XX.X%)	XX (XX.X%)
Sensitivity to light	n (%)	XX (XX.X%)	XX (XX.X%)	XX (XX.X%)
Irritability	n (%)	XX (XX.X%)	XX (XX.X%)	XX (XX.X%)
Headache	n (%)	XX (XX.X%)	XX (XX.X%)	XX (XX.X%)
Heartburn	n (%)	XX (XX.X%)	XX (XX.X%)	XX (XX.X%)
Fatigue	n (%)	XX (XX.X%)	XX (XX.X%)	XX (XX.X%)

N: Number of subjects in specified treatment group

n: Number of subjects with data available

%: Percentage based on N

RUN: DDMMYYYY HH:MM <1MED > Page X of Y

 1MED Regulatory & Clinical Development	Form	Form No.	1M-DMST-011-01-A1
	Statistical Analysis Plan	Page	Page 49 of 69
		Effective Date	07/05/2018

Table 21. AEs of Special Interest in the Multidose Phase (Safety set)

	Statistic	Treatment A (N=XXX)	Treatment B (N=XXX)	Total (N=XXX)
Total	n (%)	XXX (XXX.X%)	XX (XXX.X%)	XXX (XXX.X%)
Insomnia	n (%)	XX (XX.X%)	XX (XX.X%)	XX (XX.X%)
Elevated levels of liver enzymes	n (%)	XX (XX.X%)	XX (XX.X%)	XX (XX.X%)
Rash	n (%)	XX (XX.X%)	XX (XX.X%)	XX (XX.X%)
Nausea	n (%)	XX (XX.X%)	XX (XX.X%)	XX (XX.X%)
Upper abdominal pain	n (%)	XX (XX.X%)	XX (XX.X%)	XX (XX.X%)
Dizziness	n (%)	XX (XX.X%)	XX (XX.X%)	XX (XX.X%)
Sensitivity to light	n (%)	XX (XX.X%)	XX (XX.X%)	XX (XX.X%)
Irritability	n (%)	XX (XX.X%)	XX (XX.X%)	XX (XX.X%)
Headache	n (%)	XX (XX.X%)	XX (XX.X%)	XX (XX.X%)
Heartburn	n (%)	XX (XX.X%)	XX (XX.X%)	XX (XX.X%)

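### Elevated liver enzymes are a monitored safety sign with their own SAP rows, but no liver enzyme is named as a test and the laboratory scope is contradictory, so a zero in those rows could mean not measured

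*Protocol*

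**What the plan says.** **The risk and the promise.** Protocol 6.3 reports that "research has detected elevated levels of liver enzymes in people taking doses of 300 mg per day for long periods of time". Protocol 7.2 puts the finding among the secondary (safety) variables, in a list that opens "Symptoms and signs like mild insomnia, elevated levels of liver enzymes, rash" and promises close monitoring. Section 12.8 repeats the list. SAP 5.2.2 and 5.2.2.1 treat the same items as adverse events of special interest, and Tables 20 (single dose) and 21 (multidose) each have a row "Elevated levels of liver enzymes". Percentages in those tables are based on the number of subjects in the treatment group.

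**The laboratory content.** Protocol 10.5.1 to 10.5.3 schedule a safety laboratory analysis at V1 to V5 without saying what it contains. Section 10.6.9 itemises it under one analyte heading, Hematology: "RBC count, WBC count (total, i.e, leucocyte count and differential, i.e., neutrophils, eosinophils, basophils, lymphocytes, monocytes), platelet count, hemoglobin, hematocrit". Its sample-handling paragraph adds a glucose tube and "3.5 ml Vacutainers® (serum chemistry"), but assigns no analyte to the chemistry tube.

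**The scope elsewhere.** The synopsis describes "clinical laboratory tests (hematology, serum chemistry"). Section 12.9.1 describes "clinical laboratory tests (hematology) and adverse events including assessment of relationship to the IP". Section 10.7, on early termination, has "blood laboratory analysis (Hematology,) to be performed at investigator discretion".

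**The output.** Protocol 12.9.2 promises individual laboratory data, summary statistics and counts outside the normal range. SAP 5.2.2 reduces the secondary variables to vital signs and adverse events. The SAP's contents list (8.1) shows no laboratory table or listing, and SAP section 6 declares no change from the protocol.

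**The concern.** An enzyme level is a laboratory value and enters the data only if someone assays it. The documents promise to watch for an elevation and reserve a place to report it, but they do not say that the assay is run. A site that works from the itemised list in 10.6.9, and from the haematology-only wording of 10.7 and 12.9.1, could comply without assaying a liver enzyme.

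The safety of one month of daily intake is a secondary objective (Protocol 7.1). If no elevation is reported, the tables print zero over the whole group. A reader would take that as reassurance about the once-daily and twice-daily regimens, and no other planned output would show whether anyone was tested. An elevation that occurred in an untested subject would also go unrecorded.

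**Working it through.** The plan gives no figure on this point (no event rate, and no power calculation behind the 24 subjects), so there is nothing to reproduce. The check is a comparison of the text, followed by a short calculation of what a zero could mean.

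**1. Is a liver enzyme named as a test?** No. The list in Protocol 10.6.9 is haematological. So are the pharmacodynamic analytes in 10.4.3 and 10.6.12 (reticulocytes, red cells, haemoglobin, haematocrit). AST appears only in the abbreviation lists of the two documents.

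**2. Is serum chemistry in scope?**

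| Place | Scope |
|---|---|
| Protocol 3.1 Synopsis, Safety | haematology and serum chemistry |
| Protocol 10.6.9, sample handling | chemistry and glucose tubes drawn |
| Protocol 10.6.9, analyte list | haematology only |
| Protocol 10.7 | haematology, at discretion |
| Protocol 12.9.1 | haematology |

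Two places provide for chemistry. Two sections and the analyte list point to haematology alone. No text resolves the conflict.

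**3. Can a measured elevation reach the table?** Yes. Protocol 11.1.1 requires a value beyond the alert limits at any visit after screening to be recorded as an adverse event, unless the parameter already deviated at screening. The route exists, but it needs a measured value and a screening value to compare with.

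**4. Would the SAP output show that nothing was measured?** No. Tables 20 and 21 count reported events over all subjects in the group. Laboratory outputs number 0 of 28 tables and 0 of 25 listings.

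**5. What does a zero mean?** Suppose m subjects had an enzyme measured and none was elevated. The exact one-sided 95% upper limit for the true rate is 1 − 0.05^(1/m).

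- m = 24: 1 − 0.05^(1/24) = 0.117, or 11.7%
- m = 12: 1 − 0.05^(1/12) = 0.221, or 22.1%
- m = 0: no information; the limit is 100%

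The Total column prints 0/24 in all three cases, assuming all 24 are in the safety set.

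**6. What could full measurement show?** The chance of at least one case in n subjects is 1 − (1 − p)^n. The documents give no p, so the rates below are assumptions.

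| Assumed p | n = 12 | n = 24 |
|---|---|---|
| 1% | 11% | 21% |
| 5% | 46% | 71% |
| 10% | 72% | 92% |

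For example, 1 − 0.95^24 = 0.708 and 1 − 0.99^24 = 0.214.

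**The case against.** The strongest reply is that the protocol does provide for chemistry. The synopsis says so, 10.6.9 draws the tube at the laboratory visits, the investigator must judge every out-of-range value, and 11.1.1 turns an alert-limit deviation into an adverse event. A laboratory given that tube might well run liver enzymes. This part stands. A reader might infer from the analyte list that the trial measures haematology only, that the liver-enzyme rows must be empty, and that the chance of detecting an elevation is nil. The documents do not support that: they leave the chemistry content undefined and contradictory, and either the chemistry sample or an unscheduled test could produce an entry.

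The reply can also point to exposure. The protocol ties the finding to 300 mg per day over long periods and says no liver toxicity has been reported, whereas subjects here take 100 or 200 mg per day for 28 days. This is one sign among eleven, within a secondary objective of an exploratory study. That limits how much any zero could show: at an assumed 1% rate, testing all 24 subjects would find a case only 21% of the time. It does not answer the point, because the protocol itself chose to monitor this sign and the SAP chose to tabulate it.

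Finally, Tables 20 and 21 print counts and percentages without intervals, so the limits in step 5 are not planned output. They only show how differently the same printed zero could be read.

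**Conclusion.** The point holds as a contradiction and a gap in specification, carried through to the SAP. A named, monitored safety sign has no specified measurement; the documents disagree on whether the relevant class of test is done; and the laboratory output that would expose the gap is missing from the SAP without being declared as a change. A zero in the liver-enzyme rows therefore cannot be read as absence of a hepatic signal. Equally, it cannot be read as proof that nothing was measured.

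Its size is an ambiguity rather than a bias that can be calculated: the same 0/24 is compatible with an upper limit anywhere from 11.7% (all assayed) to 100% (none assayed). The detection probabilities are illustrative, since the documents supply no event rate. The primary pharmacokinetic analysis is unaffected. The conclusion rests on the text as supplied, in which the SAP flow chart has no readable content and was not used.

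**What to change.** 1. **Reconcile the scope.** Make the synopsis, 10.6.9, 10.7 and 12.9.1 agree on whether serum chemistry is part of the safety laboratory.
2. **State the content.** In 10.6.9, list the chemistry analytes run on the tube already drawn and the existing visits at which they are run, including the liver enzymes that the protocol says it monitors.
3. **Restore the output.** Add the 12.9.2 laboratory summaries, individual data and out-of-range counts to the SAP, or record their removal and the reason in SAP section 6.
4. **Correct the denominator.** In Tables 20 and 21, base the liver-enzyme row on subjects with a liver-enzyme measurement in that phase and print that number. If none was taken, mark the row as not assessed.

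The protocol changes belong before dosing starts, and the SAP changes before it is signed ahead of database lock. The cost is routine assays on at most 24 × 5 = 120 samples of blood already drawn, a small amount of extra SAP output, and the wording. No extra visit or venepuncture is needed. If the sponsor decides not to run chemistry, items 1, 3 and 4 still apply, and the monitoring statements in 7.2 and 12.8 need to be brought into line.

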10.6.10 IP administration

IP will be administered at site by the subject on Day -7 by intake of 1 IP capsule of 100mg, under investigator's supervision.

Subjects should be fasted for at least 10 h prior to and 2 h after administration. Water will not be permitted 1 hour before dosing dose and 1 hour post dosing.

Per protocol IP dose is 100mg.

10.6.11 Pharmacokinetic assessments

Pharmacokinetic parameters will be assessed in serum. For pharmacokinetics analyses blood samples will be collected for the analysis of plasma coenzyme Q10 before dosing and over the

	Study Title	Bioavailability Study of COQUN ORAL FORMULATION (CoQ10) administered in Healthy Adults (CoQ10-01)		
	Study ID	VF-BAQ10/2018	Sponsor:	VISUFARMA SpA
	Date	March 03, 2018	Vers.	Final

next 12 hours: at 1, 2, 4, 8 and 12 hours after intake on the single dose period (day -7) and at each following ambulatory visit.

4 ml of blood will be collected in blood collection tubes. Each blood sample will be allowed to clot for 20-25 minutes at room temperature. Then they will be centrifuged for 15 minutes at 1300g at 4°C. Afterwards the plasma will be separated into the secondary sample tubes as follows: 0.5 ml plasma into two cryotubes, one to be send to the pharmacokinetic laboratory and one back-up. The plasma cryotubes will be appropriately labeled (study code, treatment period, subject number, sampling time) and stored at -20°C to -80°C at the study center until shipment to the specified laboratory. The backup cryotubes will be kept at the study center at least until the confirmation from the pharmacokinetic laboratory that the samples arrived in good conditions.

10.6.12 Pharmacodynamics assessments

Pharmacodynamic parameters will be assessed in blood.

For pharmacodynamics blood samples will be collected for the analysis of reticulocytes, hematocrit (HCT), hemoglobin (Hb) and red blood cells during hospitalization on Day -7 and at each following ambulatory visit.

Blood will be drawn within \pm 2 minutes for dose sampling and within \pm 30 minutes for post dose sampling.

For the analysis of reticulocytes, red blood cells, haematocrit and haemoglobin, blood samples (3 ml) will be collected in 3 ml EDTA Vacutainers. Samples will remain at room temperature and will be transferred, for assay, at room temperature as well to laboratory.

The sampling tubes will be appropriately labeled (study code, treatment period, subject number, sampling time) and stored at room temperature at the study center until shipment to the specified laboratory.

10.6.13 Hospitalization

The subjects will be hospitalized for at least 12 hours for the single dose phase, therefore subjects will remain at site for around 24 hours.

Subjects will be offered a dinner for the evening before entering the single dose phase.

10.6.14 Ambulatory visits

Subjects must return to the study center for blood sampling for pharmacokinetic and pharmacodynamic assessments at each planned ambulatory visit of the multidose phase: V2 (day 0), V3 (day 7), V4 (day 14) and V5 (day 28).

	Study Title	Bioavailability Study of COQUN ORAL FORMULATION (CoQ10) administered in Healthy Adults (CoQ10-01)		
	Study ID	VF-BAQ10/2018	Sponsor:	VISUFARMA SpA
	Date	March 03, 2018	Vers.	Final

10.6.15 Meals schedule

During hospitalization (V1, day -7) a dinner will be served at around 8 o`clock in the evening. If subject will remain until next day hospitalized, on next day 1 a breakfast will be served before leaving.

Water will not be permitted 1 hour before IP intake.

10.6.16 Subject restrictions during the study

During informed consent review at screening and at each study visit, subjects will be informed and reminded of the following restrictions:

- No strenuous physical exercise (e.g., weight training, aerobics, football), sunbathing or sauna bathing for 7 days before dosing until after the end-of-study evaluation.
- No alcohol for 72 hours before dosing until after the end-of-study evaluation.
- No consumption of foods or beverages that contain grapefruit 7 days before dosing until after the end-of-study evaluation.
- Intake of xanthine (e.g., caffeine) containing food or beverages must be discontinued 24 hours before dosing. Consumption of such foods and beverages (i.e., coffee, tea, soda, chocolate) or poppy seeds is not permitted at any time while the subjects are hospitalized. If a violation occurs during the domicile period, it must be noted in the source documents and CRF.
- No other food will be consumed at any time during hospitalization.
- No concomitant medication throughout the course of the study until after the end-of study evaluation
- Water will not be permitted 1 hour before visit at site.
- Before blood sampling at screening and at each ambulatory visit, the subjects will be required to fast overnight for at least 8 hours before.

